**Participants:** A power analysis was performed to estimate optimal sample size for detecting potential differences between intervention and wait-list control groups in sedentary behavior using a repeated measures design, with an alpha of 0.05, a power of 0.80, and a medium effect (0.57). Results from the G-power analysis indicated a total of 68 participants (34 per group) would be needed for the proposed study but we have increased sample size in anticipation of a potential attrition rate of approximately 20% (a minimum of 80 adults older than 55 yrs will be recruited). Four counties (Rock, Iowa, Vilas & Dane) will each recruit between 20–30 older adults who will be randomized to either the intervention group ( $n = 10–15$ ) or the control group ( $n = 10–15$ ). Inclusion criteria includes > 55 yrs, currently inactive or low active (i.e., < 60 min of physical activity/week), residents of Rock, Iowa, Vilas or Dane Counties, and residing in a home or an apartment. Exclusion criteria are low levels of sedentary behavior (i.e.,  $\leq 6$  hours/day); recent hospitalization (past month); uncontrolled medical conditions including uncontrolled hypertension (BP > 170 systolic or 100 diastolic), heart disease (symptoms of angina with minimal exertion in the past month), actively receiving chemotherapy or palliative care for cancer, stage 4 liver disease (e.g., cirrhosis with ascites or encephalopathy or history of

bleeding esophageal varices), end-stage renal disease (on dialysis or creatine > 4), or end-stage pulmonary disease (dyspnea at rest or with minimal exertion); severe arthritis or any orthopedic condition that could be made worse by standing up and moving more; inability to stand up without assistance of another person; and inability to speak or hear spoken English. Participants will be given a gift card up to \$50 upon study completion (\$20 for participating in the study plus \$10 per each of three assessments).

Recruitment of Participants: Staff from Aging Units in the four counties will recruit older adults from their counties for this study. Recruitment strategies include announcements in senior newsletters, at congregate dining sites, churches, and medical clinics. In addition, announcements will be posted on Aging Unit websites, and flyers will be sent to mailing lists of older adults in the various counties. These strategies were used in our pilot research and worked well in recruiting the estimated sample size.

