*Demographic and Health History Questionnaire*: At baseline, participants will be asked to complete a questionnaire regarding health status and demographic information (date of birth, sex, race, ethnicity, education, and marital status), current physical activity, smoking status, and current alcohol intake.

*Mediators of Behavior Change*: As suggested by NIH reviewers, we have added selected mediators of behavior change. Participants will complete questionnaires assessing self-regulation strategies, self-efficacy, and outcome expectancies.

*Adherence to the Intervention and Outcome Assessments*: Adherence to the *Stand Up and Move More* intervention workshop will consist of participants attending at least 50% of the sessions. As for outcome assessments, adherence to wearing the accelerometers will be defined as wearing the monitors 4 out of 7 days.

*Analyses*: The primary sedentary behavior outcome variables include total sedentary time, time spent sitting in long bouts (i.e.,  $\geq 60$  minutes), and sit-to-stand transitions as measured by the activPAL. These outcomes will be examined adjusting for monitor wear time if wear time differs between groups. We will also be able to analyze changes in specific domains of sedentary behavior (e.g., watching TV, reading) from data obtained from the sedentary behavior questionnaire. A 2 (groups) x 3 trials (pre, post-1, and post-2) repeated measures ANOVA will be used to examine differences between groups in changes in sedentary behavior before and following the intervention and control conditions. Similarly, for the secondary variables of physical activity, functional performance, health-related quality of life, and mediators of behavior change, a series of 2 x 3 repeated measures ANOVA's will be performed. Significant main effects and interactions will be assessed with planned contrasts. Effect sizes will be calculated to examine the magnitude of differences between groups as well as the magnitude of change from pre to post-intervention according to methods described by Cohen. In addition,

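### The 68 participants match a group main-effect calculation averaged over all three visits, so the stated 80% power is not tied to the group-by-time comparison or to the baseline-adjusted model in the plan

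*Combined protocol and SAP*

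**What the plan says.** The Participants paragraph of Research Design and Methods describes a power analysis for between-group differences in sedentary behavior, "using a repeated measures design, with an alpha of 0.05, a power of 0.80, and a medium effect (0.57"). It continues: "Results from the G-power analysis indicated a total of 68 participants (34 per group) would be needed". Recruitment is then raised to at least 80 for attrition. The paragraph does not say which G*Power routine was run, whether 0.57 is Cohen's d or f, how many measurements were entered, or what correlation between visits was assumed.

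On the primary outcome, the Analyses paragraph says: "A 2 (groups) x 3 trials (pre, post-1, and post-2) repeated measures ANOVA will be used to examine differences between groups in changes", with planned contrasts to follow significant main effects and interactions. A note at the end of that paragraph adds longitudinal models of the two post-intervention visits, with the baseline value as a covariate and workshop as a random effect. The plan does not say which of the two analyses is primary.

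**The concern.** A power figure describes one test under one pattern of effects. Comparing arms on change is a group-by-time question. A group main effect in a three-visit ANOVA is a different question, because it compares arm means averaged over every visit, including the one before treatment, where randomisation leaves no expected difference. If the sizing used the main effect, the printed 80% does not describe the comparison of changes.

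The stake is how a null result is read. The plan says the sample was sized for the primary outcome, so readers will take a non-significant result as coming from an 80%-powered trial. Depending on which test is primary and how strongly the visits correlate, actual power could be well below or well above that.

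**Working it through.** **Inputs from the plan.** Alpha 0.05; power 0.80; effect 0.57; 68 in total, 34 per arm; three visits (baseline, week 4, week 12).

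**Inputs assumed.** The plan gives none of these: 0.57 is Cohen's d, so f = 0.57/2 = 0.285; equal variances; one common correlation ρ between visits, 0.5 unless stated and varied below; no clustering. Power comes from the noncentral F distribution.

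**Step 1: reproduce 68.** For the between-factors test with m = 3 visits, λ = f²·N·m / [1 + (m − 1)ρ], with 1 and N − 2 df.

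- N = 66: λ = 0.285² × 66 × 3 / 2 = 8.04, power 79.8%.
- N = 68: λ = 0.285² × 68 × 3 / 2 = 8.28, power 81.0%.

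The smallest even N reaching 80% is therefore 68. At ρ = 0.5 the other routes tried do not give 68. The generic within-between interaction with f = 0.285 gives 22, and a two-sample t-test gives 100 (two-sided) or 78 (one-sided). Reading 0.57 as f gives 24 or fewer in every repeated-measures routine tried.

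**Step 2: what that test implies.** With no baseline difference and 0.57 SD at both later visits, the three-visit average is (0 + 0.57 + 0.57)/3 = 0.38 SD. The main-effect test then has λ = 17 × 0.38² / (2/3) = 3.68 and 47% power at N = 68. For the average to be 0.57 SD with equal baselines, both later differences must be 0.57 × 3/2 = 0.855 SD.

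**Step 3: group-by-time test.** For arm differences (0, 0.57, 0.57), the sum of squared deviations from their mean is 0.38² + 0.19² + 0.19² = 0.2166. Then λ = (34/2) × 0.2166 / (1 − ρ), with 2 and 132 df. At ρ = 0.5, λ = 7.36 and power is 66.9%; 92 completers would be needed for 80%. If the effect halves by week 12, power is 54%.

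**Step 4: baseline-adjusted model.** λ = 17 × 0.57² / v, with 1 and about 66 df.

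- Mean of weeks 4 and 12: v = (1 + ρ)/2 − ρ². At ρ = 0.5, v = 0.50, λ = 11.05, power 91%.
- One visit: v = 1 − ρ². At ρ = 0.5, v = 0.75, λ = 7.36, power 76%.

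**Power at 68 completers, differences (0, 0.57, 0.57), before clustering:**

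| ρ | Group-by-time | Baseline-adjusted, mean of weeks 4 and 12 | Baseline-adjusted, one visit |
|---|---|---|---|
| 0.3 | 52% | 87% | 68% |
| 0.5 | 67% | 91% | 76% |
| 0.6 | 77% | 94% | 83% |
| 0.7 | 88% | 97% | 90% |

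**Step 5: is 68 unique to Step 1?** No. The group-by-time test with (0, 0.57, 0.57) returns 68 at ρ = 0.63, a change score at ρ = 0.66, and a baseline-adjusted single visit at ρ of about 0.57. A between-factors test over the two post visits alone does so at ρ of about 0.35.

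**The case against.** The strongest objection is that the routine is inferred. The plan says only that G*Power was used with a repeated measures design, and Step 5 shows that several tests of change or of post-treatment levels also give 68 at moderate correlations. This stands. The case for the between-factors route is that it returns 68 at a correlation of 0.5 with the plan's own three visits, which is suggestive but not proof. Nor does it help to argue that a correlation of 0.6 would have made that routine return 74, because that presupposes the routine.

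A reader might infer that the sizing assumes the arms already differ by 0.57 SD at baseline. The documents do not support that. A main-effect calculation fixes the visit-averaged difference. A baseline gap follows only if the difference is also taken as constant across visits, which the plan nowhere says. Read instead as equal baselines and 0.855 SD at both later visits, the same calculation would leave the group-by-time test with 96% power at correlation 0.5 and 87% at 0.3.

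It is also fair to say that main effects appear in the ANOVA description, and that the baseline-adjusted model may be the intended primary analysis. Under that model 68 completers need not be too few. This too stands, and it is why no single power figure can be assigned to the trial.

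**Conclusion.** The concern holds as a mismatch between the power statement and the planned tests. The 68 matches a main-effect calculation that averages in the baseline visit, and the paragraph does not give enough to connect 80% to either planned analysis.

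A reader might conclude that the trial has 67% power rather than 80%. The documents do not support that as an unconditional statement. The 67% requires a correlation of 0.5, 0.57 SD at both post-intervention visits, none at baseline, 68 completers and the group-by-time test as primary. Over correlations of 0.3 to 0.7 that test runs from 52% to 88%, passing 80% at about 0.63. At correlation 0.5 the baseline-adjusted model gives 91% (mean of both visits) or 76% (one visit). Workshop clustering is left out throughout and would lower these figures.

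The point does not depend on attrition, since it applies even if all 68 complete. No printed number is shown to be miscalculated.

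**What to change.** Name one primary test. The better choice is the group difference averaged over weeks 4 and 12 from the baseline-adjusted longitudinal model already in the Analyses note. It uses both later visits, and at 68 completers it has the highest power of the planned analyses at every correlation tabulated.

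Then replace the power statement in the Participants paragraph with one computed for that test. It should assume no baseline difference, say that 0.57 is a standardised mean difference (if that is what was meant) and at which visits it applies, state the correlation, give power over a range such as 0.3 to 0.7, and include an allowance for workshop clustering. If the 2 x 3 ANOVA interaction is kept as primary instead, the statement should give its power on the same terms: about 67% at correlation 0.5 with 68 completers, with the range.

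The cost is a short recalculation and a rewritten paragraph. It requires no extra participants or procedures. The downside is that the stated power may be less favourable than 80%, especially if the interaction is kept or clustering proves material.

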## PRÉCIS

Title: Translating a ‘Stand Up and Move More’ Intervention by State Aging Units to Older Adults in Underserved Communities

Objectives: To examine the effectiveness of a *Stand Up and Move More* intervention to reduce sedentary behavior, increase physical activity, and improve functional performance and quality of life in older adults. A second objective is to examine the feasibility of implementing the *Stand Up and Move More* intervention by State Aging Units to underserved communities in the state.

Design and Outcomes: A randomized controlled trial will be conducted with older adults from four counties in Wisconsin (i.e., Dane, Rock, Iowa, and Vilas counties) randomized to intervention or wait-list control groups. Sedentary behavior, physical activity levels, functional performance, and health-related quality of life will be assessed at baseline (before the intervention begins), at week 4 (after the intervention), and week 12 (follow-up) to examine the effectiveness of the program. Feasibility of implementing the program by our community partners will be assessed via semi-structured interviews.

Intervention and Duration: The intervention consists of an introductory session, four weekly sessions (i.e., once/week for four weeks), and a refresher session at 8 weeks, and will be delivered by community partners in each county. Based on self-regulation theory, the sessions will elicit ideas from older adults regarding how they can reduce their sitting time, help them set practical goals, develop action plans to reach their goals, and refine their plans across sessions to promote behavior change.

Sample Size and Population: Eighty sedentary adults greater than 55 years of age from four counties made up predominantly of rural older adults and older African American adults will be randomly assigned to intervention (n = 40) or wait-list control (n = 40) groups.

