## RESEARCH DESIGN AND METHODS

Previous Research: With funding from the Greater Wisconsin Agency on Aging Resources, research was conducted to develop an intervention to reduce sedentary behavior and examine the feasibility of implementing the intervention by a State Aging Unit in a community setting. The research was conducted in two communities in Rock County, Wisconsin which is made up of

small urban and rural communities. The older adults in these communities had high levels of sedentary behavior (averaging almost 11 hours of their waking hours per day sitting) and their function scores were below the population average. A 4-week intervention based on self-regulation theory and designed to break up extended sitting time by standing up multiple times during the day significantly ( $p < 0.05$ ) reduced sedentary behavior (60 min/day), was associated with moderate increases in light intensity physical activity (effect size = 0.52; 35 minutes/day), and large effect size improvements in mobility (i.e., gait speed; effect size = 0.74) as well as vitality (effect size = 1.15). Importantly, reductions in sedentary behavior were sustained 4 weeks after the intervention ended. Strategies used most often included standing up during television commercials, and spreading household chores out across the day. Additional strategies included getting up to get a drink of water, and setting a timer to stand up. Twenty participants (out of a total of 25) completed the 4-week program and 90% of the participants expressed high satisfaction with the program (e.g., “What a great program. It made me realize how much I sit during the day and helped me manage my sitting time”). Also, participants indicated that breaking up sitting time was more appealing to them than increasing exercise. Further, the intervention was found to be feasible for staff to implement. The director of the Rock County Council on Aging who led the workshops stated “The intervention worked because it was simple. It is not complex and that is the beauty of it.” Thus, our pilot results are quite promising and represent the development, preliminary feasibility, and piloting stages of the *Stand Up & Move More* intervention in a small sample of older adults.

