Cost Estimate: The cost of delivering the intervention in each county will be calculated based on the following: a) cost of training the health facilitators, b) payment of health facilitators for leading the workshops, c) cost of program materials, d) cost of transporting participants to the workshop sites (to ensure that older adults without transportation will be able to participate), and e) other miscellaneous costs incurred during the workshops (e.g., room rental).

Potential Problems and Alternative Strategies: We have considered the challenge of recruiting 80 older adults into this study. Based on our preliminary research, we believe we will be able to recruit the sample size (i.e., 10-15 older adults per group in each county) needed for this project based on the following: 1) there was high interest from older adults in our preliminary research, 2) we have established good working relationships with our community collaborators who have had substantial input into the design of the current project, 3) there are good working relationships between county Aging Units and the older adults they serve in their counties, and 4) we will provide transport for older adults who require transportation to the site. Each county will provide two workshops (one for the intervention group and one for the wait-list control group) over a two year period. If we are not able to reach our recruitment target in year one (recruit 3/4 of sample,  $n=60$ ) we will offer additional workshops or expand the program to other counties in the state in year two.

Collaboration with Community Partners: The intervention we are proposing to translate statewide was designed with community collaborators to be able to be implemented by State Aging Units in community settings. Our initial community partners who were instrumental in the design of the intervention included the Greater Wisconsin Agency on Aging Resources (GWAAR) and the Rock County Council on Aging. GWAAR provides community-based aging

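### Eighty recruits less the stated 20% attrition leave 64 completers, not the 68 the power analysis requires

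*Combined protocol and SAP*

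**What the plan says.** Under Research Design and Methods, Participants, the power analysis is described as "using a repeated measures design, with an alpha of 0.05, a power of 0.80, and a medium effect (0.57" in size. The result is given as follows: "Results from the G-power analysis indicated a total of 68 participants (34 per group) would be needed for the proposed study". The same sentence then raises the number in anticipation of "a potential attrition rate of approximately 20% (a minimum of 80 adults older than 55 yrs will be recruited". The four counties "will each recruit between 20–30 older adults", which allows a total of 80 to 120.

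Elsewhere the number is 80. In the Précis, participants "will be randomly assigned to intervention (n = 40) or wait-list control (n = 40) groups". Potential Problems and Alternative Strategies opens with "We have considered the challenge of recruiting 80 older adults into this study" and treats 60 as three quarters of the sample, although it also speaks of being able to "recruit the sample size (i.e., 10-15 older adults per group in each county".

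On losses in earlier work, Previous Research reports: "Twenty participants (out of a total of 25) completed the 4-week program".

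**The concern.** The only reason given for going from 68 to 80 is attrition, so the recruitment minimum should leave 68 after the attrition it names. It does not. A reader who trusts the paragraph will believe that 80% power is protected against a 20% loss, when the stated minimum protects it only against a 15% loss. At stake are a small amount of power and the accuracy of the sample-size statement that will be carried into reports of the trial.

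**Working it through.** **Inputs from the protocol.** Required number 68 (34 per group), alpha 0.05, power 0.80, effect 0.57, attrition about 20% and minimum recruitment 80 (Participants); 40 per group (Précis); 20–30 per county in four counties (Participants); pilot completion 20 of 25 (Previous Research).

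**Inputs not in the protocol, assumed here.** The effect metric (Cohen's d, so f = 0.57/2 = 0.285), the G*Power option, the number of measurements m and the correlation r between visits.

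**Step 1: reproduce the 68.** For the between-groups effect in a repeated-measures ANOVA, λ = N·f²·m / (1 + (m − 1)r), with degrees of freedom 1 and N − 2. Take f = 0.285, m = 3, r = 0.5:

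- N = 66: λ = 8.04, power 0.798
- N = 68: λ = 66 × 0 + 68 × 0.081225 × 3 / 2 = 8.28, power 0.810

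So 68 is the smallest even total that reaches 80%. If 0.57 is read as f instead, the same option needs only 12 (r = 0), 20 (r = 0.5) or 28 (r = 1). That supports the reading as d but does not prove it.

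**Step 2: try to reproduce the 80.**

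- Completers from 80: 80 × (1 − 0.20) = 64, or 40 × 0.80 = 32 per group. Shortfall: 68 − 64 = 4, or 2 per group.
- Recruits needed for 68: 68 / 0.80 = 85. With equal arms, 34 / 0.80 = 42.5, so 43 per arm and 86 in total.
- Attrition that 80 does cover: 1 − 68/80 = 15%.
- The common slip of adding 20% to the required number gives 68 × 1.2 = 81.6, which is also above 80.
- A looser reading of the rate does not help: 18% attrition leaves 80 × 0.82 = 65.6.

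The figure of 80 is therefore not reproduced at 20%.

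**Step 3: is more than 80 committed anywhere?** The counties give 4 × 20 = 80 to 4 × 30 = 120. The Précis gives 40 + 40 = 80, and the year-one target implies 60 / 0.75 = 80. Only the lower end is a commitment.

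**Step 4: cost in power, under the Step 1 assumptions.**

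| Completers | Power | Detectable d at 80% power |
|---|---|---|
| 64 (80 recruits) | 0.785 | 0.58 |
| 68 | 0.810 | 0.56 |
| 96 (120 recruits) | 0.92 | – |

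Three other designs also give 68 when the correlation is chosen to suit: the mean of two post-baseline visits, a single-visit ANCOVA and a change score. Across all four, power at 64 is 0.775–0.787. This agreement is expected, because each was calibrated to about 80% at 68. It shows only that the loss is two to three points whichever of these lay behind the 68.

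**Step 5: the model in the Analyses note.** That note adjusts the two post-intervention visits for baseline and adds a workshop random effect. For the mean of the two visits adjusted for baseline, the variance factor is (1 + r)/2 − r² and λ = d²·(N/4) / factor, with N − 3 denominator degrees of freedom. Clustering in the intervention arm only, with 32/4 = 8 completers per workshop, divides λ by (1 + 1 + 7·ICC)/2. At N = 64 and d = 0.57:

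| Workshop ICC (assumed) | r = 0.3 | r = 0.5 | r = 0.7 |
|---|---|---|---|
| 0 | 0.850 | 0.887 | 0.962 |
| 0.05 | 0.790 | 0.833 | 0.932 |
| 0.10 | 0.733 | 0.780 | 0.896 |

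The rows with clustering are optimistic, because they ignore the few degrees of freedom that four intervention workshops provide.

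**The case against.** The strongest reply is that both inputs are soft. Attrition is approximate, 80 is a floor, and the county range reaches 120, so 85 or more recruits would remove the gap. It is true that the gap exists only near the floor. But the Précis and the recruitment plan both work to that floor, and 15% is a stretch for a rate given as about 20%.

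A second reply is that the pilot does not establish 20%. Its figure is programme completion over four weeks, the protocol does not link its rate to the pilot, and wait-list participants have no workshop to leave before week 12. This stands in part: the pilot's loss of 5 in 25 does not fix the rate here. Still, it gives no support for a lower rate, and this trial follows people for longer. The arithmetic uses the protocol's own rate in any case.

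A third is that 78% belongs to one assumed test, a group effect averaged over visits that include baseline. The group-by-time interaction, arguably the natural test of differential change, has power of 0.947 at 64 with r = 0 and 0.999 with r = 0.5, if f = 0.285 is taken as the interaction effect with three measurements. That is correct arithmetic, but that test needs only 42 or 22 participants at those correlations, so on those inputs it is not what produced 68. The point does mean that 78% must be reported with its assumptions and not as the power of the final analysis.

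Last, multiple imputation keeps everyone randomised in the analysis, and people lost after week 4 still contribute a visit. Both are true and soften the loss. Neither restores 68 completers, which is what the increase was meant to secure.

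**Conclusion.** The concern holds. At the protocol's own attrition rate, its minimum recruitment leaves 64 completers against 68 required: four too few overall, or six recruits too few with equal arms. This part needs no assumption beyond the stated figures. The consequence is modest. Power is about 0.785 instead of at least 0.80, if 0.57 is d and the between-groups option was used with three measurements and correlation 0.5. For the baseline-adjusted model, power at 64 may lie above or below 0.80 depending on visit correlation and workshop ICC, neither of which the protocol gives, so a miss is not shown there. The statement is wrong as written and should be corrected, but it does not threaten the trial.

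**What to change.** Rewrite the sample-size sentences under Participants to say that 80 recruits leave 64 completers (32 per group) at 20% attrition, with power of about 78% under named assumptions. Those assumptions are the effect metric, the G*Power option, the number of measurements and the correlation; the sponsor should give the values actually used and recompute the 78% if they differ from those assumed here. This costs one paragraph and changes nothing in the conduct of the trial.

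If the sponsor would rather keep 68 completers, the minimum becomes 86 (43 per arm). That is 86/4 = 21.5 per county, inside the existing 20–30. The Précis would then change from 40 to 43 per group, and Potential Problems and Alternative Strategies from 80 to 86, with three quarters becoming 65 (86 × 0.75 = 64.5). If the plan instead counts on attrition of 15% or less, it should say so and give the reason.

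It would also help, though it is secondary, to report power at 64 for the baseline-adjusted contrast over a stated range of visit correlation and workshop ICC.

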services to 70 counties and 11 tribes and considers interventions to increase physical activity a high priority area. For this reason, GWAAR funded our preliminary research which consisted of developing the intervention and conducting preliminary testing in two communities in Rock County, WI. The results indicated significant reductions in sedentary behavior, moderate improvements in physical activity, as well as large improvements in mobility and vitality. As a result of these findings, [name] from GWAAR, who as the Community Research Associate with the Community-Academic Aging Research Network (CAARN) works with research faculty and counties in Wisconsin put out a call to identify community partners who would be interested in participating in the proposed research. Thus, our community partners have expressed high interest in this project. In addition, there is high need in these counties. For example, Vilas County currently ranks 56 out of 72 while Rock County ranks 62 out of 72 in county health rankings. The directors of the Aging Units in these counties see the “Stand Up & Move More” intervention as a viable intervention for older adults in their counties with compromised health and physical limitations. While Iowa County ranks higher in the county health rankings (29 of 72), they have identified a lack of access to physical activity programs as a significant health risk factor. In addition, there are significant health disparities in Dane County. For example, African Americans in Dane County have higher rates of cancer, diabetes, disability, and physical inactivity than any other racial/ethnic group (HealthyDane.org). Therefore, we are including the older African American community from Madison, WI in the proposed project. An African American Program Manager will be hired to recruit and facilitate the project in the community. As recommended by African American community leaders, focus groups with older African American adults will first be conducted to ensure the intervention is culturally relevant and sensitive to the needs of the community. A facilitator from the UW Survey Center who is experienced in running focus groups will conduct 2 focus groups of 8-10 older African American adults. Results will be used to market and tailor the intervention to older African American adults. An African American facilitator will be hired and trained to deliver the intervention.

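### Nothing in the plan excludes or identifies people who already took the pilot programme in Rock County, so they could be randomised to either arm and could dilute the contrast

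*Combined protocol and SAP*

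**What the plan says.** The Participants section sets the inclusion criteria: age over 55, under 60 minutes of physical activity a week, residence in one of the four counties, and living in a home or apartment. The exclusions begin "Exclusion criteria are low levels of sedentary behavior" (6 hours a day or less) and continue with recent hospitalisation and medical, functional and language criteria. Under Recruitment of Participants, the telephone screen is built on those same criteria.

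Under Previous Research, the pilot of this 4-week programme enrolled 25 people, of whom 20 completed it. Its location is given as follows: "The research was conducted in two communities in Rock County". Rock is one of the four trial counties and is to supply 20 to 30 participants. Of the recruitment channels, the plan says: "These strategies were used in our pilot research and worked well in recruiting the estimated sample size".

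For the analysis, "A 2 (groups) x 3 trials (pre, post-1, and post-2) repeated measures ANOVA will be used" to compare change between groups. A further note under Analyses adds longitudinal models with the pre-intervention value as a covariate.

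**The concern.** A trial against a wait-list control is meant to compare people given the programme with people who have not had it. Someone who completed the pilot has already been taught goal setting, action planning and self-monitoring of standing. In the intervention arm, that person may have less left to gain. In the control arm, joining the study and being assessed may prompt that person to use the techniques again. Either would pull the estimated difference toward zero.

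The plan would neither prevent this nor reveal it afterwards. Randomisation is blocked on age only, and neither the baseline questionnaire nor the schedule of assessments includes an item on earlier participation. The same Aging Unit network and the same channels are used in Rock County, so some overlap is plausible.

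**Working it through.** **1. Could a former pilot participant pass screening?** No listed inclusion or exclusion criterion mentions earlier exposure, and the telephone screen adds nothing to the list. The sitting criterion would not reliably remove them. The pilot communities averaged almost 11 hours a day, and the pilot reduced this by 60 minutes. That leaves about 11 − 1 = 10 hours, well above the 6-hour cut-off.

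**2. The plan's own sample size.** The plan states "a total of 68 participants (34 per group) would be needed for the proposed study", for alpha 0.05, power 0.80 and an effect of 0.57. Two assumptions reproduce it: 0.57 is Cohen's d (so f = 0.57/2 = 0.285), and the correlation between visits, which is not stated, is 0.5. For the between-groups F test with m = 3 visits, the noncentrality is λ = f²·N·m / (1 + (m − 1)ρ). At N = 68 this is 0.081225 × 68 × 3 / 2 = 8.28, and 68 is the smallest even N that reaches 80% power. The stated figure is reproduced. An exclusion for pilot participation would not change it.

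**3. Which route causes dilution?** Suppose a control carries a stable reduction c from the pilot. Sitting time is lower by c at baseline and at both later visits, so the change from baseline is (b − c) − (b − c) = 0, as for any other control. The change comparison and the baseline covariate largely absorb this. What remains is less further gain in intervention participants, or new gain in controls who restart the techniques during the 12-week wait.

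**4. Illustration.** Let p be the share of the sample that took the pilot, split evenly between arms. Let r be the share of the between-arm difference still achievable among them. Both are assumptions.

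- Diluted effect: d′ = 0.57 × [1 − p(1 − r)]
- Power, scaled to the stated 80%: Φ(2.802 × d′/0.57 − 1.960), where 2.802 = 1.960 + 0.842

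| Pilot participants among 80 | p | d′, r = 0 | Power, r = 0 | d′, r = 0.5 | Power, r = 0.5 |
|---|---|---|---|---|---|
| 0 | 0 | 0.570 | 0.80 | 0.570 | 0.80 |
| 2 | 0.025 | 0.556 | 0.78 | 0.563 | 0.79 |
| 5 | 0.0625 | 0.534 | 0.75 | 0.552 | 0.775 |
| 10 | 0.125 | 0.499 | 0.69 | 0.534 | 0.75 |

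Example (5 people, r = 0): d′ = 0.57 × 0.9375 = 0.534, and power = Φ(2.802 × 0.9375 − 1.960) = Φ(0.667) = 0.75.

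For scale, 5 people would be 5/25 = 20% of everyone who started the pilot, and 10 would be 40%. Ten would fill a third to a half of Rock County's 20 to 30 places.

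**The case against.** The strongest reply is that this is speculative. No passage says that any pilot participant will enrol. The documents show persistence of the pilot effect only to 4 weeks after it ended. People still sitting about 10 hours a day have ample room to change, so r = 0 is an extreme assumption. The activity criterion might also screen out some who kept their gains. All of this stands, and it is why the size is given as an illustration with r = 0.5 alongside. It does not close the gap: anyone who passes the activity criterion after losing the gains has still had the programme before.

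Two stronger readings are tempting, and the documents support neither.

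- A reader might infer that each control who kept the full pilot effect removes that person's share of the contrast. Step 3 of the working shows otherwise: a stable reduction is already present at baseline.
- A reader might count the Dane County participants as exposed too ("2 focus groups of 8-10 older African American adults"). Collaboration with Community Partners describes those groups as checking cultural relevance and helping to market and tailor the programme. It does not describe them as delivering it. Excluding 16 to 20 willing people from a county that needs 20 to 30 recruits would have a real cost with no documented exposure to justify it.

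**Conclusion.** The gap is real and limited to the pilot. Following the plan as written would allow people already treated with the programme to be randomised, without identifying them. Dilution is possible but not established: it depends on how many enrol and on what effect remains to them, and the documents give neither.

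With 5 to 10 such people among 80, the illustrative power runs from 0.775 down to 0.69, against 0.80 with none. These figures assume an even split between arms, unchanged outcome variability and exactly 80% power without dilution. The share p would be smaller if recruitment went above the minimum of 80.

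There is little slack to absorb a loss. At 20% attrition, 80 recruits leave 80 × 0.80 = 64, below the 68 required. This is a low-severity point, worth making because it is so easily closed.

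**What to change.** Add to the exclusion criteria in the Participants section: *previous participation in the Stand Up & Move More pilot workshops*. Add the matching question to the telephone screen. Do not extend the exclusion to focus-group members.

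The cost is one criterion and one question. At most 25 people are removed from the recruitment pool, all from Rock County, and the stated sample size does not change. If the sponsor prefers not to exclude them, the minimum is to ask at screening, record the answer and prespecify a sensitivity analysis without those participants.
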